## **6.9 Study Vaccine Administration**

On Day 1 before randomization, the medical history, including physical exam (if indicated by updated medical history) and vital signs, and concomitant medications will be collected, females of childbearing potential must have a negative urine pregnancy test, and information updated in the subject file to recheck subject eligibility. Immediately prior to study vaccine administration, the following biological samples will be collected: blood for hematology and chemistry, urine for urinalysis (and if applicable, pregnancy test), and serum for immunogenicity. Once these procedures are performed, study vaccine will be administered. All doses of study vaccine are 0.5 mL in volume and are administered by IM injection with a Sponsor-provided 1 mL syringe and Safety Hypodermic Needle Eclipse 1.5 inch 25 gauge as described above or PCV20 PFS, using universal precautions and sterile technique. All injections will be administered into the deltoid muscle. Injections will be administered by an unblinded staff member delegated by the Investigator.

## **6.10 Acute Observation**

The subject will be monitored by blinded study staff for signs of an acute adverse reaction for at least 30 minutes after the injection and the blinded study staff will document any AE. Vital signs will also be obtained at least 30 minutes after the injection.

Allergic reactions to the study vaccine are possible; therefore, appropriate drugs and medical equipment to treat acute anaphylactic reactions must be immediately available and a medically qualified study team member trained to recognize and treat anaphylaxis must be present in the clinic during the entire post-dosing monitoring period.

### **6.11   Solicited Adverse Events**

Solicited AE will be collected for 7 days after vaccine administration, starting on Day 1. Solicited AE for this study are local events of pain, erythema (redness) and edema (swelling) at the injection site, and systemic events of oral temperature  $\geq 100.4^{\circ}\text{F}$ , fatigue, headache, muscle pain, and joint pain.

Subjects will be trained to complete an electronic diary (eDiary) via Zelta's electronic Patient Reported Outcomes (ePRO) system. The eDiary collects the primary safety endpoint data. This system is accessed via a secure URL and will be used to observe, measure, and record these solicited AE. A digital thermometer will be provided to the subject to measure oral temperature each day, and it is to be recorded daily in the diary. To record injection site local reaction, a ruler will be provided to the subject to measure the diameter of redness and swelling at the largest point of the reaction each day; it is to be recorded daily in the diary. Study staff will be provided with a Reference Guide for instructing subjects on accessing the Zelta ePRO system. Each user will be provided with login credentials and a temporary password. The Zelta ePRO system is web-based and accessed via a secure URL.

Study staff will review the signs and symptoms recorded in the diary and the action taken for the event during the subject's clinic visit. The electronic diary will serve as the primary source document and data will be automatically integrated into the subject visit Solicited AE form in the EDC platform for site staff view-only access. The Investigator will then assess all recorded solicited events for severity and relatedness. Severity will be graded according to the FDA Toxicity Grading Scale ([FDA, 2007](#)). The results of the Investigator's assessment, if different from the subject's entry, will be recorded in a separate eCRF specified for Investigators. For solicited injection site reactions, the relationship to study vaccine will be automatically recorded to be probably related, however, the Investigator will determine the relationship for each systemic solicited reaction.

Symptoms continuing beyond the solicited AE collection period (7 days following injection) will be collected and recorded as unsolicited AE in the source document. The start date of unsolicited AE will be equal to the date of onset of the solicited AE.

## **6.12 Unsolicited Adverse Events**

Unsolicited AE (any AE not listed in the diary) will be collected for this study. Details regarding definitions, evaluation, reporting periods, and documentation are outlined in Section 8.

## **6.13 Prior and Concomitant Medications and Procedures**

At the Screening visit, the details of prior and concomitant medications and procedures (through 30 days prior to Day 1) usage will be collected, including history of vaccinations. From Day 1 through Month 1, the details of all concomitant medications and procedures including those associated with solicited AE and unsolicited AE, not qualifying as SAE, NOCI or MAAE, will be collected.

Concomitant medications and procedures associated with an SAE, NOCI, and MAAE will be collected through the end of the study.

## **6.14 Prohibited Medications and Therapies**

Subjects must not have received or be planning to receive:

- Licensed or investigational pneumococcal vaccine.
- Investigational agents or study product from 30 days prior to Day 1 through the duration of the study.
- Other (non-pneumococcal) licensed vaccines from 30 days prior to Day 1 through Month 1.
- Blood or blood product (including IGIV) from 90 days prior to Day 1 through the duration of the study.
- Systemic immunosuppressant therapy (e.g., chemotherapeutics) and immunostimulants.
- Immunomodulatory medications (e.g., oral corticosteroids, allergy shots) from 30 days prior to Day 1 through Month 1 or received systemic corticosteroids (except for inhaled, topical, intra-articular) exceeding physiologic replacement doses from 14 days prior to Day 1 through Month 1.

The history of all prohibited medications at any time during study participation (regardless of association with an AE) will be collected.

## **6.15 Emergency Unblinding**

The Investigator may obtain a treatment assignment for a study subject only in the case of a medical emergency in which knowledge of the treatment is necessary for management of an AE.

The Investigator must notify the Medical Monitor (and as backup, Medical Director) no later than 24 hours following unblinding. Additional details for this unblinding process are provided in the Pharmacy Manual.

## **6.16 Protocol Deviations**

The Investigator and delegated staff are responsible for conducting the study in accordance with the protocol. Any deviation from the protocol must be documented in the study file. Unblinded study personnel will document protocol deviations in a blinded manner for the blinded study personnel to record in the EDC. In addition, deviations must be reported to the IRB as applicable. Subject-specific deviations must be recorded in the subject's source documents. The Sponsor will review all protocol deviations on an ongoing basis and will be responsible for categorizing protocol deviations.

## **6.17 Dosing Errors**

The Investigator or designee must report any error in the dosing of study vaccine to the site-assigned unblinded CRA and Sponsor Medical Monitor or designee within 24 hours of the Investigator's awareness of the error. Additional information regarding the dosing error may be provided as a follow-up report. A dosing error without signs or symptoms is not considered an AE but may be determined to be an important protocol deviation and investigated further.

## **6.18 Study Completion for Individual Subjects**

An individual subject is considered to complete study participation after completion of the Month 6 visit (180 days after study vaccine administration) and completion of any required safety follow-up.

## **6.19 Early Termination**

An individual subject is considered to undergo Early Termination if the subject stops study participation before the Month 6 visit.

An enrolled subject may voluntarily withdraw consent for further participation at any time before the Month 6 visit. The Investigator will request (but cannot require) such subjects to provide the reason(s) for withdrawal of consent and to undergo an Early Termination visit.

In addition, the Investigator, at his or her discretion, may withdraw a subject from further participation in the study. Criteria for withdrawal by the Investigator include:

- Noncompliance with the protocol
- Pregnancy
- Immediate hypersensitivity reaction associated with a study injection

- Lost to follow-up status requires documentation of at least 3 unsuccessful attempts to contact the subject. Lost to follow-up will be determined after the date of the subject's projected last visit.
- Other reason(s) which, in the opinion of the Investigator, indicate that continued participation in the study is not in the best interest of the subject.

The Investigator or designee must report any early termination for safety reasons to the Sponsor Medical Monitor or designee within 24 hours of discontinuation. Additional information regarding ongoing AE may be provided as a follow-up report.

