**Treatment and Duration of Treatment**

Treatment comprises a single IM injection of VAX-31 or a single IM injection of PCV20.

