## 3. Objectives and Endpoints

### 3.1 Primary

The primary objectives are:

- To evaluate the safety and tolerability of a single injection of VAX-31 at 3 dose levels administered to healthy adults 50 years of age and older.
- To compare the safety of VAX-31 to that of PCV20 administered to 4 age groups:
  - Subjects 50 to 59 years of age
  - Subjects 50 years of age and older
  - Subjects 60 years of age and older
  - Subjects 65 years of age and older

Safety and tolerability will be assessed by measuring the incidence of solicited local and systemic AE, unsolicited AE, serious adverse events (SAE), new onset of chronic illness (NOCI), and medically attended adverse events (MAAE):

[REDACTED]

[REDACTED]

[REDACTED]

- Percentage of subjects reporting solicited local reactions within 7 days after vaccination (redness, swelling, and pain at injection site) in each age group
- Percentage of subjects reporting solicited systemic events within 7 days after vaccination (fever, headache, fatigue, muscle pain, and joint pain) in each age group
- Percentage of subjects reporting unsolicited AE within 1 month (30 days) after vaccination in each age group
- Percentage of subjects reporting SAE within 6 months after the vaccination
- Percentage of subjects reporting NOCI within 6 months after the vaccination
- Percentage of subjects reporting MAAE within 6 months after vaccination

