## **8.4 Follow-up of Adverse Events**

The Investigator must follow all AE until resolution, until the condition stabilizes or is no longer clinically significant, or until no further information is likely to be obtained.

The Investigator is responsible for ensuring the conduct of any supplemental investigations considered necessary to evaluate the AE. These may include unscheduled clinical laboratory tests or investigations, histopathological examinations, or consultation with other health care professionals.

[figure not shown]
In the event of a non-fatal SAE, subjects will be instructed to contact the Investigator (or designee) immediately. All subjects experiencing an SAE will be evaluated by the Investigator or designee as soon as is feasible following the report of the SAE by the subject. In the event of a fatal SAE, the Investigator must provide the Sponsor with any available post-mortem findings, including histopathology.

Additionally, the Sponsor may request that the Investigator perform or arrange for the conduct of supplemental investigations for 1 or more AE.

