## 8.7 Other Events Requiring Immediate Reporting

### 8.7.1 Pregnancy

The Investigator or designee must report all pregnancies to the Vaxcyte Clinical Safety Team within 24 hours of becoming aware of the pregnancy, using the Pregnancy Report Form. All pregnancies will be followed to outcome. Additional information regarding the pregnancy may be provided as a follow-up report.

An uncomplicated pregnancy is not considered an AE. Complications of pregnancy may qualify as AE or SAE and would therefore be documented and reported as specified above.

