6.2.6. Missing, Unused, and Spurious Data

Binary endpoints / Continuous data:

Missing data are assumed to be missing at random and ignorable. Missing data will not be estimated or imputed. Denominators for percentages will be based only on the number of subjects with non-missing values.

The only exception are some derived Day 1 to Day 7 endpoints for solicited AEs. Additional details for handling of missing data in these cases can be found in Section 6.5.1.1.

Dates:

For partial or missing AE start dates the following imputation rules will be applied:

1. If year is not missing and is after the year of first dose:
 - a. If month is missing, then month will be imputed as January.
 - b. If day is missing, then day will be imputed as the first of the month.
2. If year is not missing and is the same as the year of the first dose:
 - a. If month is missing, then impute the month as the month of the first dose date.
 - b. If day is missing, and the month is the same as the month of the first dose date, then impute day as the day of the first dose date.
 - c. If day is missing but month is after the month of first dose date, then impute day as the first day of the month.
3. If year is missing, then impute the year as the year of the first dose date:
 - a. If month is missing, then impute the month as the month of the first dose date.
 - b. If day is missing, then impute the day as the day of the first dose date.
4. If the start date is completely missing, but the AE is either ongoing (i.e. AE stop date is missing) or the stop date is after the first dose date then impute the start date as the first dose date.
5. For any cases involving the rules above, if the AE end date is before the AE start date, then do not impute the AE start date and assume that the AE is treatment emergent/concomitant for the purpose of the analysis. Further, if the AE stop date occurs prior to the first dose date, do not impute the AE start date, and assume that the AE is not treatment emergent.

No imputations will be applied to AE stop dates or other dates. As indicated above, AEs with missing stop date are considered ongoing.

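### Protocol 6.19 lets the investigator end a vaccinated subject's participation, including for a vaccine reaction, and nothing then captures new SAE, NOCI or MAAE through Month 6

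*Protocol*

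**What the plan says.** Protocol 6.19 (Early Termination) states that the investigator, at discretion, "may withdraw a subject from further participation in the study". The reasons listed are noncompliance, pregnancy, "Immediate hypersensitivity reaction associated with a study injection", loss to follow-up, and an open category for other reasons bearing on the subject's best interest. The same section requires early terminations for safety reasons to be reported within 24 hours, so safety-driven termination is foreseen.

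The synopsis fixes the regimen: "Treatment comprises a single IM injection of VAX-31 or a single IM injection of PCV20".

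Protocol 3.1 lists among the primary endpoints "Percentage of subjects reporting SAE within 6 months after the vaccination", and NOCI and MAAE over the same period. Three sections govern how these are collected:

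- Protocol 8.5.1 runs SAE reporting from consent for as long as the subject participates.
- Protocol 7.1.6 collects SAE, NOCI and MAAE by telephone at Months 2 to 6.
- Protocol 7.2 asks subjects who stop before Month 6 to attend one Early Termination visit, where unsolicited AE and SAE are reviewed.

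Two sections continue some follow-up regardless. Protocol 8.4 says "The Investigator must follow all AE until resolution, until the condition stabilizes or is no longer clinically significant", and Protocol 8.7.1 says "All pregnancies will be followed to outcome".

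On analysis, SAP 6.2.6 says "Missing data are assumed to be missing at random and ignorable". It rules out imputation for these endpoints and bases denominators on subjects with non-missing values. SAP 5.4 does not replace subjects who stop after vaccination.

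**The concern.** In a multi-dose trial, an immediate reaction is a natural reason to give no further doses. Here a subject who reacts has already had the only dose, so withdrawal from the study stops only observation. The primary SAE, NOCI and MAAE percentages run to Month 6, and the rule permits observation to end because of an event the vaccine may have caused.

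Reaction rates could differ between the three VAX-31 dose levels and PCV20, so any such loss could differ by arm. Because the decision is discretionary, practice could also vary between the roughly 25 sites. What is at stake is a small number of subjects, but they are ones in whom later safety information is of particular interest.

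**Working it through.** **What is collected after an investigator withdrawal.** Take a vaccinated subject withdrawn before Month 6.

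| Information | Collected after withdrawal? | Source |
|---|---|---|
| The reaction itself and any AE already reported | Yes, followed to resolution or stabilization | Protocol 8.4 |
| An existing pregnancy | Yes, to outcome | Protocol 8.7.1 |
| Events up to termination | Yes, if the subject attends the requested visit. NOCI and MAAE are not named there, but the SAP records them as unsolicited AE | Protocol 7.2; SAP 6.5.1.2 |
| A new SAE after termination | No; the reporting period ends with participation | Protocol 8.5.1 |
| A new NOCI or MAAE after termination | No; these come from the Month 2 to 6 calls | Protocol 7.1.6 |

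No section keeps such a subject on the call list.

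**Share of the window lost.** With a 180-day window and withdrawal on day d, the share lost is (180 − d)/180:

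- Day 1: 179/180 = 99.4%
- Day 8: 172/180 = 95.6%
- Day 30: 150/180 = 83.3%

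An immediate reaction would fall at the first of these.

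**The plan's own figure.** The documents give no withdrawal rate and no precision target for the 6-month endpoints. The only safety calculation is the Stage 1 detection probability in Protocol 10.1 (16 per arm), and it reproduces: 1 − 0.85^16 = 92.6% and 1 − 0.90^16 = 81.5%, against the stated 92% and 81%. The present point does not depend on it.

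**Size, for illustration.** Inputs are 250 per arm (Protocol 10.3) and the VAX-24 rates through 6 months in Protocol 2.1 (SAE 1.2%, NOCI 1.9%, MAAE 11.3%), assumed to carry over to VAX-31.

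Expected subjects per arm:

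- SAE: 250 × 0.012 = 3.0
- NOCI: 250 × 0.019 = 4.75
- MAAE: 250 × 0.113 = 28.25

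*If withdrawal is unrelated to later events.* The chance of seeing at least one SAE in an arm is 1 − (1 − 0.012)^250 = 95.1%. Removing 12 subjects entirely gives 1 − (1 − 0.012)^238 = 94.4%. The effect is negligible.

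*If a withdrawn subject would have had a first SAE later.* The arm moves from 3/250 = 1.2% to 2/250 = 0.8%. Dropping the subject from the denominator instead gives 2/249 = 0.8%, so the denominator convention hardly matters. In the 65-and-older group, a minimum of 200 subjects over four arms is about 50 per arm, and one subject is 1/50 = 2 percentage points.

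*How often to expect that.* Assume 2 to 10 investigator withdrawals among 1000 subjects, a range not taken from the documents. That is 0.5 to 2.5 per arm. Expected missed SAE subjects per arm:

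- At the 1.2% rate: 0.5 × 0.012 = 0.006 to 2.5 × 0.012 = 0.03
- At ten times that risk (12%): 0.06 to 0.3

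**The case against.** The case against making much of this is substantial, and most of it stands.

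- **A reader might infer that all three named criteria remove subjects because of a safety outcome.** The text does not support that. Withdrawal is permitted, not required. Protocol 8.1.1 and 8.7.1 state that an uncomplicated pregnancy is not an AE, and noncompliance is not a safety event. Both can also apply before dosing, since enrollment occurs at randomization and SAP 5.4 provides for discontinuation between randomization and vaccination. Only the hypersensitivity criterion is necessarily post-dose and itself a safety outcome.
- **A reader might infer that 6.19 contradicts Protocol 8.4 and 8.7.1.** It does not. Those duties can run alongside withdrawal, and 6.19 itself allows follow-up reports on ongoing AE. They are partial safeguards that stop short of new events.
- **A reader might infer that the missing-at-random assumption is violated.** That is too strong. Missing at random allows missingness to depend on observed data, and a recorded reaction is observed. The criticism that survives is narrower: an unadjusted percentage by arm makes no use of that information.
- **A reader might infer that the subject disappears from the safety analysis.** Under SAP 4.1 the Safety Population excludes only subjects lost at Day 1 who report no AE, so a subject with a recorded reaction stays in and counts for it. If the reaction was an SAE, the subject is already counted among those with any SAE. A later NOCI or MAAE could still be missed.
- **The number affected is probably very small.** Protocol 2.1 reports no related SAE or NOCI with VAX-24, and Protocol 4.4.2 excludes a history of severe allergic reaction.

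None of this supplies collection of new primary-endpoint events after withdrawal. That gap remains, and a written rule opens it.

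**Conclusion.** The point holds in a limited form. Protocol 6.19 permits discretionary loss of primary safety follow-up in an already vaccinated subject, in one listed case because of a reaction to the vaccine. No section captures new SAE, NOCI or MAAE from withdrawal to Month 6, and the SAP's unadjusted percentages do not account for loss linked to a reaction.

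The expected numerical effect is small. The shift from 1.2% to 0.8% in an arm of 250 shows what one missed SAE subject would do; it is not a forecast. It rests on the VAX-24 rate carrying over and on a withdrawn subject later having a first SAE. The documents give no withdrawal rate, so the actual effect cannot be calculated, and no planned dose decision or comparison has been shown to depend on it. This is a cheap improvement, not a flaw that threatens the trial's conclusions.

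**What to change.** Reconcile Protocol 6.19 with the 6-month primary safety endpoints by adding one sentence. For any vaccinated subject whom the investigator withdraws for any listed reason, including the open category for other reasons, follow-up for SAE, NOCI and MAAE continues by the scheduled monthly calls through Month 6 unless the subject withdraws consent or is lost to follow-up. Protocol 8.5.1 should use the same end point, so that SAE reporting does not stop at investigator withdrawal.

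The criteria need not be deleted. Removing some of them would leave the open category in place and the gap with it. Noncompliance that affects serology is already handled by exclusion from the Immunogenicity Evaluable Population (SAP 4.1 and 4.2). The change concerns data collection only and proposes no clinical management rule.

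The cost is a wording change and a few extra telephone calls on a schedule that already exists.

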## **6.20 Study Completion: Overall**

The study is planned to be completed after all subjects have completed the Month 6 visit (or Early Termination, as appropriate), all necessary safety follow-up has been completed, and all data have been monitored and queries have been resolved. The Sponsor reserves the right to terminate the study prior to the planned study completion.

# **7. Study Procedures by Visit**

The overall summary of procedures and assessments by visit is provided in the Schedule of Events ([Appendix A](#)). All visits are relative to the day of vaccine administration, Day 1. Acceptable time windows for the visit schedule are indicated.

